8.3. Benefits

There are no proven benefits from participation in this study and usage of the investigational device.

The study may indirectly be of benefit to study participants if they are determined to be a frequent asymptomatic shedder of HSV-2 and, therefore, a potential transmitter of infection while not having symptoms

Possible benefits for future people using the VIBLOK cream will be based upon results of this and other studies of VIBLOK.

Information gained from the conduct of this study may be of benefit to patients with the same medical condition in the future. The long-term results of using the VIBLOK cream are not known at the present time. There are no alternative treatments. The Clinical Investigator's Brochure has a full assessment of the clinical risk associated with the VIBLOK cream.

8.4. Risk-Benefit Analysis

Use of VIBLOK according to the instructions is expected to reduce the risk for HSV-2 transfer from one person to the other via skin-to-skin contact during sexual intercourse. However, as indicated in section 8.3 there is no proven benefit for the study participants.

Participants enrolled in this clinical study will be at risk of those events listed in section 8.1.2. These risks are considered at an acceptable level with no known residual risk as all VIBLOK ingredients have been used for many years, and the ingredient zinc oxide is listed in the European Pharmacopeia (also refer to the VIBLOK Investigator's Brochure). All adverse events will be carefully monitored throughout the study.

Hence it is believed that the participants participating in this study are not at greater risk than any other people with an HSV-2 infection.

8.5. Definitions

The definitions used in this protocol are consistent with those referenced in ISO 14155:2011.

Term	Definition	Reference/Justification
Adverse Event (AE)	Any untoward medical occurrence, unintended disease or injury, or untoward clinical signs (including abnormal laboratory findings) in subjects, users or other persons, whether or not related to the investigational device.	ISO 14155: 2011

Term	Definition	Reference/ Justification
Serious Adverse Event (SAE)	
Adverse Event that:
 
 a) led to a death, b) led to a serious deterioration in the health of a study subject that 
 • resulted in a life-threatening illness or injury, • resulted in permanent impairment of a body structure or body function, • required in-patient hospitalization or prolongation of existing hospitalization, • resulted in a medical or surgical intervention to prevent permanent impairment to body structure or a body function. c) leads to fetal distress, fetal death or a congenital abnormality or birth defect 
The following is not considered an SAE: Hospitalization for diagnostic or elective surgical procedures, planned at or before the enrollment for a pre-existing condition.
	ISO 14155: 2011
Adverse Device Effect (ADE)	
Adverse event related to the use of an investigational medical device.
 
This definition also includes adverse events resulting from insufficient or inadequate instructions for use, deployment, implantation, installation, or operation, or any malfunction of the investigational device. And events resulting from use error or from intentional misuse.
	ISO 14155: 2011
Serious Adverse Device Effect (SADE)	Adverse Device Effect that resulted in any of the consequences characteristics of a Serious Adverse Event.	ISO 14155: 2011
Unanticipated Adverse Device Effect (UADE)	Any serious adverse effect on health or safety or any life-threatening problem or death caused by, or associated with, a device, if that effect, problem, or death was not previously identified in nature, severity, or degree of incidence in the investigational plan or application (including a supplementary plan or application), or any other unanticipated serious problems associated with a device that relates to the rights, safety, or welfare of patients.	ISO 14155: 2011
Device Malfunction or deterioration	Failure of a device to perform in accordance with its intended purpose when used in accordance with the manufacturer's instructions.	GHTF/SG2/N 54R8:2006
Endpoints, Clinical Safety (after 26 days)	
 • SADE incidence • Nature, frequency, duration, severity, seriousness and causality of adverse events 	
Endpoints, Performance (after 26 Days)	
 • Comparison of HSV detection rate on days with asymptomatic shedding prior and after applying VIBLOK • Comparison of HSV copy number on days with asymptomatic shedding prior and after applying VIBLOK 	
Pre-Existing Condition	A pre-existing condition is one that is present at the start of study treatment. A preexisting condition is not an adverse event unless it worsens as a result of the study treatment.	
Recurrent Hospitalization Re-Hospitalization	Re-hospitalization for HSV-2 recurrences and/or complications related to the cream.	

9. Statistical Considerations

This clinical study is a prospective, non-randomized, comparative multi-center safety and performance trial.

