5.2.2. Participant Screening - Visit 0-1

The screening of potential participants will be conducted by one or more study team members. The site research team will be responsible for ensuring and reporting screening of men and women for study eligibility. Cumulative screening and enrollment logs will be maintained by research sites. Reasons for screen failures will be documented in study logs.

All anti-viral therapies shall be stopped minimally 7 days prior to Visit 1.

Women that are more than 1 year post-menopausal will be considered as having no child bearing potential, and the pregnancy test and use of contraceptives is not applicable for them.

Table 2 lists the schedule of events for participants from the initial screening and baseline measures through their bi-weekly follow-up visits. These measures are more fully described in the subsequent sections.

Table 2. Schedule of Events

Activity	Treatment Period				
	Screening	Visit 1	FUP call	Visit 2	Visit 3
Informed Consent	X				
Review Inclusion/Exclusion Criteria	X				
Medical History (including HSV history)	X				
Interim History (including HSV history)		X		X	X
Targeted Physical Exam (including external genital exam)	X	X*		X*	X*
HSV serology	X				
Urine pregnancy test	X				
Provide Study Device and/or training		X	X	X	
Review device use adherence				X	X
AE assessment				→	
User Questionnaire					X
Daily Swab Collection & Diary				→	

* for women possibly including internal genital exam if symptomatic

The following screening data will be collected for all study subjects prior to enrollment to assess possible eligibility:

- Medical history, standard of care physical examination, including external genital exam

A subject will be considered as "enrolled", once (s)he has signed the Informed Consent. Study

specific data will not be collected for subjects who fail any of the eligibility criteria and do not apply the study product; these subjects will be recorded on a Screening Log where the reason for screening failure will be documented.

5.2.3. Treatment start - Visit 1

Once participant's eligibility is confirmed, i.e. HSV-2 serology is positive, select assessments and laboratory tests will be done prior to document baseline status. These include:

- Physical examination, including a genital examination that for women may include an internal genital examination if symptomatic;
- (Interim) medical history;
- Urine pregnancy test;
- Adverse Events assessment

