7.1. Definitions

An Adverse Event (AE) is any untoward medical occurrence, unintended disease or injury, or untoward clinical signs (including abnormal laboratory findings) in subjects, users or other persons, whether or not related to the investigational medical device.

A Serious Adverse Event (SAE) is any adverse event that:

- a) leads to death
- b) leads to a serious deterioration in the health of the subject that
 1. results in a life-threatening illness or injury
 2. results in a permanent impairment of a body structure or a body function
 3. requires in-patient hospitalization or prolongation of existing hospitalization
 4. results in medical or surgical intervention to prevent permanent impairment to a body structure or a body function
- c) leads to fetal distress, fetal death, congenital abnormality or birth defect

Adverse Device Effects and Serious Adverse Device Effects are those AEs and SAEs that occur as an untoward or unintended response to a medical device. These events include those which result from insufficiencies or inadequacies in the Instructions for Use or deployment of the device as well as user error.

Unanticipated Serious Adverse Device Effect (USADE) is defined as any serious adverse effect on health or safety or any life-threatening problem or death caused by – or associated with – the device, if that effect, problem or death was not previously identified in nature, severity, or degree of incidence in the investigational plan (including documents such as the protocol, Investigator's Brochure, informed consent form or other study-related documents), or any other unanticipated serious problem associated with the device that relates to the rights, safety or welfare of subjects.

Adverse events may be volunteered by participants, elicited from questioning by Investigator or designee, or collected via observation by the Investigator. In addition, participants will be instructed to contact the investigator, and/or study coordinator if any significant adverse events occur between study evaluation visits.

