7.2. Adverse Event Assessments

The Investigator will determine whether or not the event is related to the device and/or procedure, and whether or not the event meets serious criteria. Pre-existing medical conditions or symptoms reported prior to the participant's enrollment will not be recorded as an AE. In the event there is a worsening in the pre-existing medical condition or symptoms then an AE must be recorded.

If it is determined that an AE has occurred, the investigator should obtain all the information required to complete the study AE Form. The causal relation of the event to either the investigational device or to the procedure will be categorized by the Investigator as follows:

None – AE is not associated with the investigational device or procedure.

Remote – AE had minimal or no temporal relationship to the use of the investigational device and/or a more likely alternative etiology exists.

Possible – AE had a strong temporal relationship to the use of the investigational device or procedure and there is no contradicting evidence that can reasonably explain the subject's condition.

Probable or Definite – AE had a strong temporal relationship to the use of the investigational device or procedure and another etiology is highly unlikely.

All AEs will be reviewed by the Study Safety Officer. The AE will be assessed as to its seriousness and relationship to the device, the procedure, and whether it was anticipated or not anticipated.

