#### 5.2.2 Display of adverse events

All adverse events occurring after initiation of study treatment (including events likely to be related to the underlying disease or likely to represent concomitant illness) will be displayed in summary tables.

The tables will list each adverse event, the number of participants in whom the event occurred, and the rate of occurrence.

Adverse events will be grouped by the following categories:

- Any event
- Bleeding / Anaemia
- Bowel
- Cardiac
- Malignancies
- Miscellaneous
- Neurological
- Pulmonary
- Renal
- Urogenital
- Vascular
- Genital

- Skin
- Infection
- Trauma
- Other

The analysis of adverse events comprises the following categories:

- Any adverse event
- Any adverse event by consideration
- Adverse events considered to be a toxic reaction
- Adverse events considered to be an allergic reaction
- Adverse events considered to be an infection
- Adverse events considered to be other
- Any adverse event by severity
- Possibly, probably or definitely related to investigational device adverse events
- Possibly, probably or definitely related during application of the investigational device adverse events
- Possibly, probably or definitely related after application of the investigational device adverse events
- Possibly, probably or definitely related to study procedure adverse events
- Adverse events related to a pre-existing / other medical condition
- Adverse event related complications associated with an HSV 2 infection
- Any adverse event
- Recurrence of genital herpes
- Systemic symptoms
- Fever
- Headache
- Malaise
- Myalgia(s)
- Local pain and itching
- Dysuria
- Tender lymphadenopathy
- Unanticipated adverse events
- Adverse events by action taken
- No action taken
- Drug Therapy
- Any
- Prescription
- Non-Prescription
- Surgical intervention or other invasive therapy
- Hospitalization
- Other treatment / procedure
- Withdraw from study due to AE
- Adverse events by outcome
- Resolved
- Resolved with sequelae
- Ongoing
- Ongoing at time of exit
- Unknown / Lost to Follow-up

- Death
- Reportable adverse events

Serious adverse events will only be listed as it will be expected that there will only be very few or no serious adverse event.

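### Protocol 7.2 and 8.5 conflict on whether worsening of a pre-existing condition is an adverse event when the investigator judges it unrelated to the cream

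*Protocol*

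**What the plan says.** Two places in the protocol govern pre-existing conditions.

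- **Protocol 7.2 (Adverse Event Assessments)** first excludes the baseline state: "Pre-existing medical conditions or symptoms reported prior to the participant's enrollment will not be recorded as an AE". It then covers change: "In the event there is a worsening in the pre-existing medical condition or symptoms then an AE must be recorded". No causal condition is attached. The investigator grades causality on a scale that runs from None and Remote upwards, and a second look follows: "All AEs will be reviewed by the Study Safety Officer".
- **Protocol 8.5 (Definitions, Pre-Existing Condition)** sets its own reference point: "A pre-existing condition is one that is present at the start of study treatment". It then states: "A preexisting condition is not an adverse event unless it worsens as a result of the study treatment".

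The general AE definition in Protocol 7.1 covers events "whether or not related to the investigational medical device". The AE entry in the 8.5 table has the same scope.

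The SAP does not restate the rule for pre-existing conditions. SAP 5.2.2 displays all AEs after the start of treatment, including those probably due to the underlying disease or to concurrent illness. It plans a category for AEs related to a pre-existing or other condition. Among HSV-2 complications it plans a line for "Recurrence of genital herpes".

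**The concern.** A site cannot follow both rules. If a participant's pre-existing condition worsens and the investigator does not blame the cream, 7.2 demands an AE record and 8.5 says there is no AE.

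The 8.5 wording also reverses the usual order, in which the event is recorded first and its relatedness judged afterwards. Under 8.5 the investigator's first view of causality decides whether a record exists at all, and a view that leaves no record cannot be reviewed. The study is single-arm and open-label and is meant to support CE marking, so the AE data should not depend on which section a site happened to read. An event that was never recorded cannot be restored at analysis.

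**Working it through.** The plan gives no figure on this point, so the check is a comparison of text, followed by a short calculation that shows how far the primary endpoint could be touched.

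**Step 1. Where the rules differ**

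| Situation | 7.1 and 7.2 | 8.5 | Agreement |
|---|---|---|---|
| New event, related or unrelated | AE | AE (general AE entry) | Yes |
| Worsening of a pre-existing condition, caused by the cream | AE | AE | Yes |
| Worsening of a pre-existing condition, judged unrelated | AE must be recorded | Not an AE | **No** |
| Condition first appearing between consent and first application | Not pre-existing, so an AE | Pre-existing | **No** |

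The third row is the main conflict. The fourth comes from the reference dates. Protocol 5.2.2 says: "A subject will be considered as 'enrolled', once (s)he has signed the Informed Consent". Protocol 5.3 allows Visit 1 to follow consent by up to just under 21 days, and 7.4 starts AE reporting at enrollment. A condition that arises in that interval is therefore classified differently by the two sections.

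**Step 2. Which text stands alone**

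The 8.5 entry is the outlier. The AE definitions in 7.1 and in the 8.5 table itself do not depend on causality. The scale in 7.2 has levels for unrelated events, which would be pointless if such events were not recorded. The 8.5 entry for serious adverse events (SAEs) exempts only diagnostic or elective hospital stays planned at or before enrollment for a pre-existing condition, which implies that unplanned stays for such conditions count. The SAP 5.2.2 tables presuppose that unrelated events reach the database.

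**Step 3. What follows if a site applies 8.5**

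An SAE is defined as a kind of AE. A worsening that is not an AE therefore cannot be an SAE, however severe. It would fall outside 24-hour reporting (7.4), Safety Officer review (7.2), the data monitoring committee's review of SAE rates (10.3) and the SAE listing (SAP 5.3.1.2).

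For the secondary safety endpoint the direction is clear. The AE count falls. Among worsenings of pre-existing conditions, those judged unrelated drop out while those judged related stay, so the tabulated causality shifts towards related.

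**Step 4. Reach into the primary endpoint**

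SAP 5.2.1 calls the study a success if the upper limit of the two-sided exact 95% interval for SADE incidence is below 10%. With x events in n participants, the Clopper-Pearson upper limit is the 0.975 quantile of Beta(x + 1, n − x). For x = 0 this equals 1 − 0.025^(1/n).

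- 0/36: 1 − 0.025^(1/36) = 9.74%, which agrees with the planned 36.
- 0/46: 1 − 0.025^(1/46) = 7.71%, success.
- 1/46: 11.53%, failure. At n = 42 one event gives 12.57%, and at n = 36 it gives 14.53%.

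One SADE therefore decides the result at any planned size. This describes the success rule and is not an estimate of the effect of the 8.5 wording. For that wording to change the result, a worsening would have to be serious, be called unrelated by the investigator, go unrecorded because of 8.5, and be one that review would have reattributed to the cream.

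**The case against.** The strongest defense is that 8.5 is one line in a definitions table, while the operative text (7.1, 7.2 and SAP 5.2.2) points the other way. Most sites would probably work from 7.2. Recurrences in particular would still be seen through the daily diary, lesion swabs, unscheduled visits and the SAP summaries of outbreaks and lesion days. Protocol 8.1.1 lists them among the risks and adverse events of the disease. This stands as far as it goes: the clinical information on recurrences would not be lost. Their classification as AEs would still be open, and other pre-existing conditions have no comparable diary record.

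Three stronger readings might be inferred, and the documents do not support them.

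- **That all events judged unrelated escape the safety data.** Only worsening of pre-existing conditions is affected.
- **That the loss can be counted from recurrences.** Eligibility requires at least 3 recurrences a year. Under a Poisson assumption, 1 − exp(−3 × 28/365.25) = 20.5% of participants would have at least one in 28 days, or about 9 of 46. This does not measure the difference between the rules. A recurrence at the participant's usual rate may not be a worsening under 7.2 either, so it could be a non-event under both sections.
- **That the primary result is at risk in any practical sense.** A SADE is device-related by definition, and 8.5 keeps worsening caused by treatment as an AE. All four conditions in Step 4 must hold together. The protocol also does not say that the Safety Officer's view overrides the investigator's for the endpoint.

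It is also fair to note that the secondary AE endpoint is descriptive (SAP 1.3) and that no success criterion depends on it.

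**Conclusion.** The contradiction is real, sits in current protocol text, and should be corrected. It is confined to worsening of pre-existing conditions that the investigator judges unrelated, together with a mismatch of reference dates between consent and first application.

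Its direct effect is on the completeness and causality profile of the secondary AE endpoint and on the SAP 5.2.2 tables for pre-existing conditions and HSV-2 complications. The affected class is not marginal in kind, because every participant enters with recurrent genital herpes. Its size cannot be derived from the documents: it depends on how many worsenings occur, how many are judged unrelated, and which section each site applies. The effect on the primary SADE endpoint is indirect and probably rare.

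The conclusion rests on reading both sections literally and on 8.5 carrying the same authority as 7.2. The protocol states no order of precedence.

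**What to change.** 1. In the Pre-Existing Condition entry of Protocol 8.5, delete the phrase that makes AE status depend on the study treatment. Any worsening is then recorded as an AE and relatedness is assessed afterwards, as 7.1 and 7.2 already provide.
2. Use one reference date for pre-existing in 7.2 and 8.5. Enrollment would match the start of AE reporting in 7.4.
3. State in the protocol that genital herpes recurrences after treatment start are recorded as AEs, as SAP 5.2.2 assumes. The first change alone does not settle this, because a recurrence at the usual rate may not count as a worsening.

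The cost is a few words of protocol text and a somewhat higher reported AE count. The sample size, the primary analysis and the planned SAP tables stay as they are.

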4.1. Inclusion Criteria

Candidates for this study must meet **all** of the following inclusion criteria:

1. Participant is male or female and at least 18 years of age
2. HSV-2 seropositive by the UW Western blot or Alegria assay
3. History of recurrent genital herpes with at least 3 recurrences in the last year or, if currently on suppressive/ prophylactic therapy, prior to starting the therapy (antiviral therapy has to be stopped at least 7 days prior to initiation of the trial product).

4. General good health at the discretion of the investigator.
5. Willing to not use any topical genital therapy aside from the study device for the duration of the trial.
6. Willing to not use any systemic anti HSV therapy during the entire study starting 7 days prior to baseline.
7. Willing to obtain 2 swabs from external-genital areas once daily for the duration of the trial.
8. Willing to keep a daily trial diary during the treatment period.
9. Negative pregnancy test for women at screening.
10. Willing to use contraceptives for the duration of the study.
11. Subject must be willing and able (in the opinion of the investigator) to understand the patient information and informed consent form and to comply with the clinical trial protocol and procedures.
12. Subject must be willing to give written informed consent.

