8.1.1. Risks/ Adverse Events associated with the disease state

Complications associated with an HSV-2 infected population may include, but are not limited the following:

- Recurrences of genital herpes
- Systemic symptoms, including fever headache, malaise and myalgia's
- Local pain and itching
- Dysuria
- Tender lymphadenopathy

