At visit 1 the actual medical history status will be presented, i.e. the data from the screening visit including the changes reported at Visit 1.

- History of genital herpes

- Years since first date of diagnosis of genital herpes
- How was the diagnosis "genital herpes" made (Clinical / Culture or PCR / Blood test)
- Type of blood test performed (Alegria assay / UW Western blot / Other )
- The number of recurrences of genital herpes the participant had in the past year ( today –1y)
- Years since last recurrence the participant had
- Did the participant experience HSV recurrence at Visit 1 since the screening visit? (No / Yes)

- Targeted Physical Exam - General

- Height (cm)
- Weight (kg)
- Heart rate (bpm)
- Systolic and diastolic Blood pressure (mmHg)
- Genital
- Any (new) abnormalities in the inguinal and/or pubis area related to genital herpes? (Yes / No)
- Any (new) abnormalities in the peri-anal area related to genital herpes? (Yes / No)
- Any (new) abnormalities in the genital area related to genital herpes? (Yes / No)
- Any (new) obvious discharge present in the genital, peri-anal, inguinal or pubis area? (Yes / No)
- Any (new) other abnormalities in the genital, peri-anal, inguinal or pubis area, NOT related to genital herpes but relevant for the study (at the judgement of the investigator)? (Yes / No)

At visit 1 the actual targeted Genital Exam will be presented, i.e. the data from the screening visit including the new abnormalities reported at Visit 1.

- Grooming Habits

- Genital grooming habits (None / Shaving / Waxing / Other)
- Frequency of performing these extra genital grooming habits (Daily / Weekly / Monthly / Other)
- Did participant change any genital grooming since the screening visit? (Yes / No)

At visit 1 the actual grooming habits will be presented, i.e. the data from the screening visit including the changes reported at Visit 1.

- Medication vs Treatment

- Any use of medication, topical cream or other product on a continuous basis, for the treatment or maintenance of genital herpes or any other medical condition as mentioned in the medical history? (Yes / No)
- Treatment in case of an outbreak of genital herpes to alleviate/ treat the genital herpes on top of any treatment/maintenance of genital herpes on a continuous basis (No additional treatment / Prescription medication /

Nonprescription medication / (Topical) cream / Any other treatment). More than one answer allowed.

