#### Shaving and waxing habits

- The genital grooming habits in relation to the pre-VIBLOK HSV-2 sample value will be explored by descriptive statistics of the pre-VIBLOK HSV-2 sample value by grooming habit (None / Shaving / Waxing / Other) and by frequency of habit (Daily / Weekly / Monthly / Other / No Shaving habit).

- The genital grooming habits in relation to the difference between the pre and post VIBLOK HSV-2 sample value will be explored by descriptive statistics of the difference between the pre and post VIBLOK HSV-2 sample value by grooming habit (None / Shaving / Waxing / Other) and by frequency of habit (Daily / Weekly / Monthly / Other / No Shaving habit).
- Participant satisfaction using VIBLOK as assessed on the participant questionnaire Frequency distributions will be presented for
  - Ease of use of VIBLOK (Very easy to use / Somewhat easy to use / Difficult to use)
  - The use of VIBLOK (Simple and clear / Somewhat confusing / Very confusing)
  - VIBLOK user documentation (Excellent / Adequate / Inadequate)
  - Use of VIBLOK if VIBLOK was available for use (Participant would use it / Participant would use it only in very special cases / Participant would never use it)Only listings will be provided for
  - The best participant liked about VIBLOK
  - The least participant liked about VIBLOK
  - Suggestions of participant for improving VIBLOK
- Symptoms (Itching, burning, tingling / Lesions (sores, blisters, ulcers, crusts) / Other) as recorded on the participant's diary.
  - Any symptoms (Yes / No)
  - The percentage of days with any symptoms in relation to total number of days of participation.
  - Any Itching, burning, tingling (Yes / No)
  - The percentage of days with any Itching, burning, tingling in relation to total number of days of participation.
  - Any lesions (sores, blisters, ulcers, crusts) (Yes / No)
  - The percentage of days with any lesions in relation to total number of days of participation.
  - Any other symptom (Yes / No)
  - The percentage of days with any other symptom in relation to total number of days of participation.
- Location of the lesion (Genitals / Rectal (perineum, perianal) / Buttock / Other) as recorded on the participant's diary.
  - Any location (Yes / No)
  - The percentage of days with any location in relation to total number of days of participation.
  - Any rectal (perineum, perianal) location (Yes / No)

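### Protocol 8.5 counts a worsened pre-existing condition as an adverse event only if the cream caused it, Protocol 7.2 sets no such condition, and herpes recurrences may therefore be in or out of the AE counts

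*Protocol*

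**What the plan says.** Four places in the Protocol and one in the SAP bear on whether a herpes event on treatment is an AE.

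- **Protocol 8.5, Pre-Existing Condition:** "A preexisting condition is not an adverse event unless it worsens as a result of the study treatment". The condition is dated from when study treatment begins.
- **Protocol 7.2:** conditions or symptoms reported before enrollment are not AEs, but "In the event there is a worsening in the pre-existing medical condition or symptoms then an AE must be recorded". The investigator then grades causality, and the lowest grade is no association at all. Protocol 5.2.2 equates enrollment with signing consent.
- **Protocol 7.1, AE definition:** it applies "whether or not related to the investigational medical device". The AE entry in the 8.5 table says essentially the same.
- **Protocol 8.1.1:** the adverse events of the disease state include herpes recurrences and "Local pain and itching".
- **SAP 5.2.2:** the tables show all AEs after treatment starts, "including events likely to be related to the underlying disease or likely to represent concomitant illness". There are rows for herpes recurrence, for local pain and itching, and for AEs related to a pre-existing or other medical condition.

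Inclusion criterion 3 requires "History of recurrent genital herpes with at least 3 recurrences in the last year", or the same history before suppressive therapy was started. Herpes is thus a pre-existing condition in the whole treated population.

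**The concern.** Section 8.5 puts the causality judgement before the recording decision. Section 7.2 puts it after. In most trials this would affect a few incidental conditions. Here the pre-existing condition is the disease under study, and its symptoms occur where the cream is applied. The cream's own anticipated harms (Protocol 8.1.2) are hypersensitivity or allergic reactions and epithelial sensitization.

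The number and type of AEs is a secondary safety endpoint (Protocol 9.5.2), and the data are meant to support a CE application. With up to six sites, the same event could be counted at one and not at another, depending on which sentence the site follows. Under 7.2 the Safety Officer reviews every AE, so an investigator's view that an itch was herpetic can be questioned. If 8.5 keeps the event off the AE form, that review does not take place.

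**Working it through.** The plan states no figure on this point, so there is none to reproduce. The check is to apply each rule to the same events and then to size the result.

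**Applying the rules**

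1. *Genital itching worsens on treatment and is judged herpetic.* 8.5: not an AE, because the cream did not cause the worsening. 7.2: an AE, with causality graded low. SAP 5.2.2: a row is waiting for it.
2. *A lesion appears on day 12, judged herpetic, at the participant's usual frequency.* 8.5 read strictly: not an AE. 7.2: unclear, because a recurrence at the usual rate is not plainly a worsening. 7.1 alone: an AE. Protocol 8.1.1 and SAP 5.2.2: expected as an AE.
3. *Itching begins between consent and first application, and continues.* 7.2: not excluded, since it arose after enrollment. 8.5: pre-existing. This gap is under 21 days (Protocol 5.3).
4. *A worsening is judged to be caused by the cream.* An AE under every rule.

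Events 1 to 3 change status with the rule. Event 4 does not, and it is the only kind that can become a SADE. The word *worsens* also lacks a reference for itching: SAP 3.4 collects "The number of recurrences of genital herpes the participant had in the past year" but no baseline frequency of itching or burning.

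**Size of the recurrence row**

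Inputs: 46 treated participants (Protocol 9.1); 28 days (the Day 28 visit, window 26 to 31); 3 recurrences a year, the eligibility minimum. Assumptions: that rate continues on study, and recurrences follow a Poisson process with a constant rate. The range of 1.5 to 6 a year is also assumed.

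- Expected recurrences = n × rate × days/365 = 46 × 3 × 28/365 = 10.6. At 1.5 a year 5.3; at 6 a year 21.2.
- Participants with at least one = n × (1 − exp(−rate × days/365)) = 46 × (1 − exp(−0.2301)) = 46 × 0.2056 = 9.5. At 1.5 a year, 46 × 0.1087 = 5.0; at 6 a year, 46 × 0.3689 = 17.0.
- Follow-up of 26 or 31 days at 3 a year: 8.9 or 10.3 participants.
- After 15% drop-out, 46 × 0.85 = 39 participants: 39 × 0.2056 = 8.0.

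At 3 a year the recurrence row could thus read 0 of 46 if every site applied 8.5 strictly and judged every recurrence herpetic, or about 9 of 46 (19.6%) if every site recorded all of them. Confidence intervals are left out because the contrast is between two recording rules on the same events, not sampling error. The documents give no rate for itching, so that part cannot be sized.

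**The case against.** The strongest reply is that 8.5 can be reconciled with the rest. Latent HSV-2 is present when treatment begins, but a lesion that first appears on day 12 is not, and may be read as a new event under 7.1. Protocol 8.1.1 and SAP 5.2.2 make the intent plain, and 7.2 stands in the operative safety chapter while 8.5 is a glossary entry. This is a fair reading, and it makes 0 of 46 an extreme case. It does not settle the matter: 8.5 does not state that reading, nothing ranks 7.2 above 8.5, and a worsening of symptoms already present at the start (event 1) is in conflict on any reading. It is also true that SAP 5.2.2 displays AEs and does not define them, so it can only show what sites recorded.

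Three stronger inferences are not supported.

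- *That the events would go unrecorded.* A recurrence leads to a lesion swab and a clinic examination (Protocol 5.2.6). SAP 3.6 tabulates outbreaks as a reason for unscheduled follow-up and new genital abnormalities at examination. SAP 4.3.2 reports "The percentage of days with any Itching, burning, tingling in relation to total number of days of participation". What could be missing is the AE entry, with its causality grade and Safety Officer review.
- *That diary symptoms are cut off from AE review.* The same site staff do both at the same visits (Protocol 5.2.5), AEs are also elicited by questioning, and participants are told to call about unusual genital symptoms. A linking sentence would only write down existing practice.
- *That the SAP 2.3 statement on not reconciling participant-measured data blocks this.* It introduces the removal of implausible measurements, and its table lists only swab data.

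**Conclusion.** The conflict between Protocol 8.5 and Protocol 7.2 is in the current text and unresolved. It concerns what is recorded as an AE in a population where everyone has the condition at issue.

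Its reach is limited. A reader might infer that the primary result is at risk. It is not: a SADE must be serious and device-related, and a worsening attributed to the cream is an AE under both rules. The AE endpoint affected is descriptive, with no hypothesis tested (SAP 1.3).

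At the assumed 3 recurrences a year, about 9 of 46 participants is an upper bound on how far the recurrence row can move over 28 days, and 5 to 17 across 1.5 to 6 a year. Mixed site practice, or sites following 7.2 in spite of 8.5, would give a smaller shift. The textual conflict itself does not depend on these assumptions.

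**What to change.** Amend Protocol 8.5 and 7.2 together:

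- In 8.5, delete the last seven words of the sentence "A preexisting condition is not an adverse event unless it worsens as a result of the study treatment", which carry the causal condition.
- Use one cut-off, the first VIBLOK application, in both sections. The start of AE reporting at enrollment in 7.4 can stay, since the cut-off only settles what counts as pre-existing.
- State that a genital herpes recurrence on study, or genital itching or burning that is new or worse for that participant, is recorded as an AE whatever the cause, with causality graded afterwards. This also settles the recurrence at usual frequency, which 7.2 leaves open.

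No change is needed to the SAP tables, the diary procedures or SAP 2.3.

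The cost is a short protocol amendment, signed as Protocol 11.6 requires and with ethics committee approval where needed. It adds roughly 11 non-serious AE forms for recurrences at 3 a year (5 to 21 across the assumed range), plus an unknown number for itching. The change makes recording consistent. In a single-arm trial it cannot by itself show whether a symptom came from herpes or from the cream.
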